4.4.3 Statistical analysis

Frequency tabulations (number and percentages) will be provided with ADA negative/positive/unevaluable samples per visit.

Frequency tabulations (number and percentages) will be provided on:

- patients per ADA patient category
- prevalence and incidence of ADA
- ADA unevaluable patients
- ADA baseline positive/negative/unevaluable samples

For details on the definitions, see the above section 4.4.2.1.

The above frequency tabulations will be repeated for NAb assay using the definitions as defined in section 4.4.2.2.

In addition, a frequency tabulation (number and percentages) will be provided of NAb positive patients within the ADA patient category (ADA negative, treatment-unaffected, treatment-induced, treatment-boosted and unevaluable).

SGS	Statistical Analysis Plan	
ARGX-113-1801	Final analysis	Final 1.0 of 28MAR2022

Correlation tables (restricted to the efgartigimod treated patients only) by ADA patient category (ADA negative, treatment-unaffected, treatment-induced, treatment-boosted and unevaluable) will be provided for the following parameters:

- mean drug concentration over time
- mean percent change from baseline in platelet count
- mean percent change from baseline in total IgG
- number and percentage of sustained platelet count response (key secondary endpoint (week 19 24) in the overall population)

The above tables will be repeated for NAb patient category as defined in previous section.

SGS	Statistical Analysis Plan	
ARGX-113-1801	Final analysis	Final 1.0 of 28MAR2022

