#### 1.2. Benefit-Risk Assessment

Efgartigimod has been shown to effectively reduce IgG antibodies in several clinical trials, including healthy volunteers, patients with MG, and with ITP.

More specifically, a phase 2 trial (ARGX-113-1603) in patients with ITP enrolled a patient population who was predominantly refractory to previous lines of ITP therapy, with the majority of patients having long-standing disease, prior ITP treatment exposure and approximately half with baseline platelet count of  $<15\times10^9/L$ .

Efgartigimod resulted in a rapid and marked reduction of IgG antibodies (maximum mean reduction of 65%) and of all IgG subtypes.

argenx BVBA Confidential Page 37 of 162

Treatment with efgartigimod, whether 5 mg/kg or 10 mg/kg, was associated with an increase in platelet counts in more patients than occurred in the placebo group, with greater numerical separation from placebo as the platelet count threshold stringency was increased. Additional post hoc analyses further supported these observations, showing a longer duration of clinically meaningful effect and statistically significantly more active-treated patients achieving a platelet count of  $\geq 50 \times 10^9/L$  for more than 10 cumulative days compared to the placebo group.

In each of the subgroups of patients based on ITP classification (newly diagnosed, persistent, or chronic ITP) or those with or without historical or concomitant use of TPO-RA, there were examples of efgartigimod-treated patients with an increase in platelet count.

In the open-label treatment period patients received 4 weekly infusions of efgartigimed 10 mg/kg, either as first exposure in patients who previously received placebo or retreatment with efgartigimed. In this part of the trial, the majority of patients (58%) had improved platelet counts.

Efgartigimod is under investigation in MG, another disease driven by IgG autoantibodies. In a phase 2 trial ARGX-113-1602, 4 weekly IV infusions of 10 mg/kg efgartigimod led to statistically significant improvements in clinical scales and were well tolerated. A phase 3 trial ARGX-113-1704 and accompanying open-label extension trial ARGX-113-1705 are ongoing in this indication.

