2.2.2 Baseline and change from baseline

The baseline value is defined as the last available non-missing value prior to first administration of the IMP. For IgG (total and subtypes), only results from IVD assays will be considered, including screening samples.

Vital signs (VS) assessments on day 1 are considered pre-dose (no assessment time collected, pre-dose per protocol).

For parameters related to questionnaires, the baseline is the last value before or at the day of first administration of the IMP, independent of the time of administration.

Change from baseline at time point t = value at time point t - baseline value.

Percentage change from baseline at time point t is defined as follows:

- When baseline value is not zero: 100*((value at time point t baseline value) / baseline value)
- When both baseline value and value at time point t are zero: 0
- When baseline value is zero and value at time point t is not zero: not calculated

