2.3.3 Rounding

Variables will be rounded to the appropriate number of decimals at display level:

- Time since diagnosis and BMI will be rounded to 1 decimal.
- Ratios will be rounded to the number of decimals of the parameter with the least number of decimals.
- Safety laboratory results will be rounded to a maximum of 3 decimals.

2.3.4 *Outliers*

There will be no outlier detection. All measured values will be included in the analyses.

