14.2.1.37	Platelet Count: Percent Change from Baseline in Count by ADA Patient Classification	n Platelet	FAS
14.2.1.38	Platelet Count: Percent Change from Baseline in Count by NAb Patient Classification	n Platelet	FAS
14.2.2.1.1	Extent of Disease Control (≥50x10^9/L): Stratif Whitney Analysis in Patients with Chronic ITP Chronic	ied Mann- – FAS	FAS- chronic
14.2.2.1.2	Extent of Disease Control (≥50x10^9/L): Stratif Whitney Analysis in Patients with Chronic ITP Chronic	ied Mann- – PP	PP- chronic
14.2.2.1.3	Extent of Disease Control (≥50×10^9/L): Stratif Whitney Complementary Analysis (Treatment F Strategy) in Patients with Chronic ITP – FAS C	ied Mann- Policy hronic	FAS- chronic
14.2.2.1.4	Extent of Disease Control (≥50×10^9/L): Stratif Whitney Sensitivity Analysis in Patients with C – FAS Chronic	ied Mann- hronic ITP	FAS- chronic

SGS	Statistical Analysis Plan		
ARGX-113-1801	Final analysis	Final 1.0 of	28MAR2022
14.2.2.2	Extent of Disease Control (≥50×10^9/L): Comp Analysis: Cox Proportional Hazards Regression Patients with Chronic ITP	lementary Model in	FAS- chronic
14.2.2.3	Extent of Disease Control (≥50×10^9/L): Kapla Estimates in the Overall Population	n Meier	FAS
14.2.2.4	Extent of Disease Control (≥50×10^9/L): Descr Statistics of Cumulative Number of Weeks of D Control by Stratification Factor, Baseline Platel and Overall in Patients with Chronic ITP	iptive Disease et Count	FAS- chronic
14.2.2.5	Extent of Disease Control (≥50×10^9/L): Stratit Whitney Analysis in the Overall Population	fied Mann-	FAS
14.2.2.6.1	Extent of Disease Control (≥50×10^9/L): Descr Statistics of Cumulative Number of Weeks of D Control by Stratification Factor and Overall in t Population	iptive Disease he Overall	FAS
14.2.2.6.2	Extent of Disease Control (≥50×10^9/L): Descr Statistics of Cumulative Number of Weeks of D Control in the Overall Population by Baseline P Count	iptive Visease latelet	FAS
14.2.2.6.3	Extent of Disease Control (≥50×10^9/L): Descr Statistics of Cumulative Number of Weeks of D Control in the Overall Population by Dosing Fre	iptive Disease equency	FAS
14.2.2.6.4	Extent of Disease Control (≥50×10^9/L): Descr Statistics of Cumulative Number of Weeks of D Control in the Overall Population by Number of Therapies	iptive Disease f Prior ITP	FAS
14.2.2.6.5	Extent of Disease Control (≥50×10^9/L): Descr Statistics of Cumulative Number of Weeks of D Control in the Overall Population by Time Sinc	iptive Disease e Diagnosis	FAS

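### Platelet effect by ADA and NAb class is summarised as mean percent change from a baseline with no floor, so the mean is sensitive to very low baselines; absolute change should be shown as well, and the NAb response table listed

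*SAP*

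**What the plan says.** SAP 4.4.3 plans a set of correlation tables by ADA patient category, limited to efgartigimod-treated patients. One of the parameters is "mean percent change from baseline in platelet count". Sustained platelet count response is in the same list. The section then says: "The above tables will be repeated for NAb patient category as defined in previous section". Table list 8.1 carries the percent-change displays as 14.2.1.37 (ADA) and 14.2.1.38 (NAb), titled "Platelet Count: Percent Change from Baseline in" platelet count.

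SAP 2.2.2 defines the denominator: "The baseline value is defined as the last available non-missing value prior to first administration of the IMP". The only rule for small denominators covers a baseline of exactly zero: "When baseline value is zero and value at time point t is not zero: not calculated". SAP 2.3.4 adds: "There will be no outlier detection. All measured values will be included in the analyses".

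Inclusion criterion 5 (Protocol 4.3.1) requires the mean of two counts to be below 30×10⁹/L and sets no lower limit. The only indication of the spread is in Protocol 1.2, which describes the phase 2 population as having "prior ITP treatment exposure and approximately half with baseline platelet count of" less than 15×10⁹/L.

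**The concern.** These tables are meant to show whether antibodies weaken the platelet effect. Percent change divides by a quantity that has a ceiling near 30×10⁹/L and no floor, so a small absolute rise from a very low baseline gives a very large percentage. Response elsewhere in the SAP is defined on the absolute scale (at least 50×10⁹/L, or at least 30×10⁹/L and 20×10⁹/L above baseline). Where a relative criterion is used, the two-fold rise in the IWG responses of SAP 4.1.2.4, it is tied to an absolute floor of 30×10⁹/L. The platelet MMRM (SAP 4.1.3.6) and the descriptive platelet tables (SAP 4.1.3) use change from baseline, not percent change. SAP 4.4.3 gives no reason for the different scale.

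Classes could be small. At most 156 patients are planned at 2:1, so about 104 on efgartigimod, spread over five ADA categories. If a few patients with very low baselines fall into one class, its mean may move for reasons unrelated to antibodies.

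There is a related gap in the table list. Sustained response by ADA class is Table 14.2.1.7.12, but the 14.2.1.7 block ends at 14.2.1.7.14 without a NAb version, although 4.4.3 calls for one. SAP 4.1.3 likewise names only the ADA classification when it describes repeats of the response table. Programming from the list alone would omit the NAb response table.

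**Working it through.** The plan states no figure to reproduce here, so the check applies the SAP 2.2.2 formula directly: percent change = 100 × (v − b)/b, with b the baseline and v the later count (×10⁹/L).

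**Single patients.**
- 2 to 10: 100 × 8/2 = +400%. Does not reach 50.
- 25 to 75: 100 × 50/25 = +200%. Reaches 50.

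One patient outscores another exactly when v₁/b₁ > v₂/b₂. A patient who only reaches 20 therefore outscores a 25-to-100 patient (ratio 4) whenever the baseline is below 20/4 = 5. A patient who reaches 49 does so below 49/4 = 12.25.

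**Two illustrative classes of ten.**

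| Class | Reach ≥50 | Mean % change | Median % change | Mean absolute change |
|---|---|---|---|---|
| Four go 25 to 100, six stay at 25 | 40% | 4 × 300/10 = +120% | 0% | 4 × 75/10 = +30.0 |
| Two go 2 to 20, eight stay at 25 | 0% | 2 × 900/10 = +180% | 0% | 2 × 18/10 = +3.6 |

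Mean percent change ranks the class with no responders higher; absolute change ranks the classes correctly. The median avoids the reversal but does not separate them. With four low-baseline patients instead of two, a geometric-mean ratio is still reversed (1.74 for the first class, 2.51 for the second), so a log scale is not a reliable remedy.

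**How often the order goes wrong.** The documents give neither the lower tail of baseline nor an ADA rate, so all of the following is assumed: 25 patients with 10% responders against 79 with 30% (104 in total); responders have a median count of 90 (log-SD 0.5); the rest stay near baseline (log-SD 0.4); 10,000 trials per setting.

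| Assumed baseline | Wrong order, mean % change | Wrong order, mean absolute change |
|---|---|---|
| Uniform 1–29 | about 9% | about 3% |
| Lognormal centred on 15, cut below 30 | about 5% | about 3% |
| Uniform 10–29 | about 4% | about 3% |

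Under uniform 1–29 with 25% responders overall, the 17% of patients with baselines of 5 or less supply about 60% of the summed percent change and 19% of the summed absolute change. Under the lognormal setting about 4% of patients are that low, and they supply about 12% of the summed percent change.

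For comparison with phase 2, uniform 1–29 puts 14/29 = 48% of baselines below 15. Uniform 10–29 puts only 5/20 = 25% there, so it is the mildest case and fits that description least well.

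**The case against.** The strongest case against the point is that nobody has to judge loss of effect from this mean.

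- Sustained response is in the same 4.4.3 list, rests on an absolute threshold, and is to be repeated for NAb. In simulations of the same kind it misordered the two classes in only about 1% of trials in every setting.
- For ADA, Table 14.2.1.7.12 also breaks response down by baseline platelet count, so an imbalance in low baselines can be seen there.
- SAP 2.4.1 puts the SD, median, quartiles, minimum and maximum beside the mean, so a skewed mean would be visible. Listings 16.2.6.2 and 16.2.6.7 give the individual data.
- Absolute change has its own skew: Protocol 4.5 provides for counts above 400×10⁹/L.

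All of this stands, and it limits the consequence. A reader might infer that a few low-baseline patients will dominate the class means, so that a real loss of effect will be hidden or a false one shown. The documents do not support that: they give an upper limit at entry and one phase 2 proportion, and dominance appears only if many baselines are in low single digits. Nor do they make mean percent change the only platelet measure by class. For NAb, the missing response table is an omission from the list, not from the planned analysis.

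What the objection does not remove is the arithmetic. The mean is the statistic that 4.4.3 names, it can rank classes against the trial's own response definition, and absolute change did no worse in any setting tried.

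**Conclusion.** The point holds as a minor improvement to descriptive tables. Mean percent change is a fragile summary when baseline has a ceiling near 30×10⁹/L and no floor, and a non-responder can outweigh a responder. The size is uncertain. Under the assumed inputs, wrong ordering of two classes is about 4% to 9%, against about 3% for absolute change; most of the excess arises when low single-digit baselines are common, and little remains when none is below 10. Even the least favourable setting orders the classes correctly in about nine trials in ten. These figures rest on assumed baseline distributions, class sizes and response rates. No primary or alpha-controlled result is affected, and it would go too far to say that the immunogenicity conclusions cannot be trusted. Separately, table list 8.1 does not carry the sustained-response-by-NAb table that 4.4.3 requires.

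**What to change.** In SAP 4.4.3 and Tables 14.2.1.37 and 14.2.1.38, report absolute change from baseline in platelet count by ADA and NAb class, beside percent change or in place of it, still limited to efgartigimod-treated patients. The variable is already derived for Table 14.2.1.20. If percent change is kept, lead with its median rather than its mean. Add to table list 8.1 a NAb version of Table 14.2.1.7.12. The cost is one added variable in two tables and one extra table, with no new data and no change to any tested endpoint.

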5. SAFETY ANALYSES

5.1 **ADVERSE EVENTS**

5.1.1 Available data

Adverse events (AEs) are coded into SOC and PTs using MedDRA version 24.1. For each AE, start and stop date/times are collected as well as severity National Cancer Institute common toxicity criteria for adverse events [NCI CTCAE] v5.0⁸), a seriousness flag, treatment relatedness, relatedness to procedures, action taken towards the study drug, outcome, and AE of special interest (AESI) category (bleeding events, infections).

5.1.2 Derivation rules

Treatment-emergent adverse events (TEAE) are defined as AEs starting on or after first administration of any study drug.

Based on their start date/time, AEs will be allocated to the phase during which they started. Each AE will therefore be reported in only 1 phase. Phases are defined in section 2.2.1. In case the AE start date/time is incomplete or missing and the AE could consequently be allocated to more than 1 phase, a worst-case allocation will be done as detailed below:

• Treatment phase versus screening phase/follow-up phase: the AE will be allocated to the treatment phase unless the available parts of the AE start or stop date/time provide evidence for allocating to the screening phase/follow-up phase.

Death is not considered an AE in itself but a 'fatal' outcome of an SAE.

An AE for which the study drug was discontinued is defined as an AE with action taken 'drug withdrawn'.

Infusion-related reactions (IRR) will be defined as all AEs with a MedDRA preferred term that are listed in either:

- MedDRA Hypersensitivity SMQ broad selection
- MedDRA Anaphylactic SMQ broad selection
- MedDRA Extravasation SMQ broad selection, excluding implants

AND occurring within 48 hours of an infusion, or within 2 days in case no AE start time is available. In case of partially missing AE start date, the AE will be considered as an IRR, unless the available parts of the AE start date provide evidence it did not occur within 48 hours of an infusion.

Two AESI types will be used: 'Bleeding events' as recorded on the CRF and 'Infections' as defined using the MedDRA system organ class (SOC) 'Infections and infestations'.

Adverse events of hypersensitivity are defined as AEs with a MedDRA preferred term listed in the MedDRA Hypersensitivity SMQ broad selection.

SGS	Statistical Analysis Plan	
ARGX-113-1801	Final analysis	Final 1.0 of 28MAR2022

Treatment relatedness will be dichotomized as follows in tables:

- Treatment related: related, probably related, possibly related or missing
- Not treatment related: not related, unlikely related

AE onset and duration will be calculated as follows when start and stop dates are fully known

- AE onset day (versus first administration) =
 - \circ AE start date \geq date of first administration: AE start date date of first study drug administration + 1 day
 - AE start date < date of first administration: AE start date date of first study drug administration
- AE duration (days) =
 - \circ AE end date AE start date + 1 day
 - Study discontinuation date AE start date + 1 day (when the AE start date is fully known but the AE is not resolved at the end of the study)
 In this case the duration will be presented as ">x days".

Event rates per patient years of follow-up (PYFU) is defined as the number of events divided by the sum of follow-up time (duration of treatment + FU phase) of all patients per treatment expressed in years.

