#### **5.4.1.** Screening and Treatment

During the screening period (up to 2 weeks) the patient's eligibility for trial participation will be evaluated.

All eligible patients will be randomized to receive IV infusions of either efgartigimed 10 mg/kg body weight or matching placebo throughout the trial.

All patients will initially receive weekly IV infusions from visits 1 to 4.

argenx BVBA Confidential Page 56 of 162

Based on the platelet counts as of visit 2, the dosing frequency can be altered from visits 5 to 16 according to the following rules (the change in dosing frequency will occur at the current visit):

- Reduce from weekly to q2w in patients achieving platelet counts of  $\geq 100 \times 10^9$ /L for 3 out of 4 consecutive visits (the fourth visit being the current visit), and have a platelet count of  $\geq 100 \times 10^9$ /L at the last of these 4 visits
  - -OR-
  - 3 consecutive visits
- Increase from q2w to weekly in patients whose platelet counts drop below 100×10^9/L on 2 consecutive visits
  - -OR-
  - $<30\times10^9/L$  at 1 visit
  - -OR-

in patients who receive rescue therapy (see Section 6.8.4)

- Temporary withholding treatment
  - o for reasons described in Section 4.5, IMP should be reintroduced once the investigator considers the undue risk to the patient has passed
  - o in patients with platelet counts greater than  $400 \times 10^9$ /L, IMP should be resumed at the 10 mg/kg q2w dose when the platelet count falls to fewer than  $150 \times 10^9$ /L
- Post-baseline platelet count can be performed within 1 day of the next procedure as per the SoA (both dosing and non-dosing visit), allowing the results to be incorporated into the criteria above.

From visits 17 to 24, the dosing frequency is fixed for each individual patient (ie, either weekly or q2w regimen), based on the regimen the patient was receiving at visit 16 or at the last visit at which IMP was administered.

Exceptions to the fixed dosing frequency are:

- Continued weekly dosing for patients requiring rescue therapy
- Continued q2w dosing for patients resuming IMP when the platelet count falls to fewer than 150×10^9/L after having had platelet counts greater than 400×10^9/L

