1.4 EXPECTED SAMPLE SIZE

Approximately 117 patients with chronic ITP and up to 39 patients with persistent ITP will be randomized in a 2:1 ratio to receive efgartigimod or placebo, respectively. Recruitment will end as from 117 patients with chronic ITP have been randomized.

SGS	Statistical Analysis Plan	
ARGX-113-1801	Final analysis	Final 1.0 of 28MAR2022

Non-Japanese patients will be stratified according to the following factors:

- History of splenectomy (yes versus no)
- Receiving concurrent ITP therapies at baseline (yes versus no)

For Japanese patients enrolled in sites in Japan, there will be no stratification, i.e. randomization will be performed within the full set of Japanese patients.

The null and alternative hypotheses are defined as H_0 : $\pi_1 = \pi_2$ versus H_A : $\pi_1 \neq \pi_2$, where π_1 and π_2 are the population probabilities to achieve a sustained platelet count response (primary efficacy endpoint) for patients with chronic ITP receiving placebo and for patients with chronic ITP receiving efgartigimod, respectively.

The response rate of placebo patients with chronic ITP reaching the primary endpoint is expected to be \mathbf{M} %, while for efgartigimod patients with chronic ITP a response rate of \mathbf{M} % is expected (i.e. $\pi_1 = \mathbf{M}$ and $\pi_2 = \mathbf{M}$). Given these assumptions, a total of N = 117 patients with chronic ITP randomized will ensure a power of at least 90% to reject the null hypothesis at a 1-sided significance level α of 0.025.

For the first key secondary endpoint "extent of disease control," assuming a median cumulative number of weeks of disease control over the planned 24-week treatment period with platelet counts of $\geq 50 \times 10^9$ /L in the chronic ITP population of 10 weeks for patients receiving efgartigimod and 3 weeks for patients receiving placebo, a total of N=117 patients will ensure a power of >99% (two-sided α of 0.05) to detect a significant difference between both treatment groups. For ensuring a power of at least 90%, a total number of N=54 patients would be needed, given these assumptions. Calculations are based on the Wilcoxon-Mann-Whitney test, where the O'Brien-Castelloe approach[§] was taken to compute the power, taking into account a 2:1 allocation ratio to receive efgartigimod versus placebo.

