2.4.3 Ordering in tables and listings

All tables will be presented per treatment, unless specified otherwise. In by-visit displays, worst-case will be shown last, if present.

In listings for general characteristics, results will be ordered by treatment and patient, unless specified otherwise.

All other listings will be ordered by treatment, patient, analysis visit, and time point, unless specified otherwise.

In tables showing several parameters, each parameter will begin on a new page and parameters will be sorted alphabetically, within the parameter category if applicable.

The efgartigimod treatment group will always be shown first, then the placebo treatment group.

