3.6.2 Derivation rules

The following parameters will be derived:

- Number of administrations: sum of all administrations of study drug.
- Compliance (%): 100*(number of doses received/number of doses expected); Compliance will be calculated over the 24-week treatment period and will take into account the weekly or q2w administration.

Notes:

- Dosing is expected at a visit except if reason not done is "DUE TO BIWEEKLY ADMINISTRATION" or "DUE TO PLATELET COUNT > 400X10^9/L"
- Only visits up to treatment discontinuation are considered in the compliance calculation.
- Cumulative duration of q2w dosing: number of weeks for which the patient was on the q2w dosing regimen
- Dosing frequency will be derived for subjects still being dosed at or after visit 17, based on dosing at CRF visits 14, 15, 16 and 17:
 - Biweekly (q2w): if the patient was not dosed at visit 15 or at visit 16
 "DUE TO BIWEEKLY ADMINISTRATION"
 - Else, Weekly: if the patient was dosed at both visit 15 and 16
 Note: in case of missing information at visit 15 and/or 16, a missed visit 15 or 16 is considered as dosed and visits 14 and 17 are also

SGS	Statistical Analysis Plan	
 ARGX-113-1801	Final analysis	Final 1.0 of 28MAR2022

taken into account. If the patient was dosed at two subsequent visits in this timeframe, dosing frequency is set to weekly.

• Else, Unknown: in case dosing frequency cannot be determined based on the above rules.

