5.1.3 Presentation of results

Tables will present TEAEs only. The AEs will be presented for the overall study duration, including AEs during the follow up. Pre-treatment AEs will only be listed.

An overview table will show the number and percentage of patients with at least 1 event and the number of events for the following:

- TEAEs
- Serious TEAEs
- Non serious TEAEs
- Grade \geq 3 TEAEs
- Fatal TEAEs
- Treatment related TEAEs according to the principle investigator
- Procedures related TEAEs
- Serious treatment related TEAEs
- TEAEs for which the study was discontinued
- TEAEs for which the study drug was discontinued
- TEAEs for which the study drug was interrupted
- TEAEs of special interest: bleeding events
- TEAEs of special interest: infections
- IRR events

In addition, the number of events per patient years on study will be added to the overview table.

SGS	Statistical Analysis Plan	
ARGX-113-1801	Final analysis	Final 1.0 of 28MAR2022

Summary tables by MedDRA SOC and PT will show the number and percentage of patients with at least 1 event. The table of TEAEs will additionally show the number of events.

Separate tables will be prepared for the following TEAEs:

- Serious TEAEs
- Non serious TEAEs
- Grade \geq 3 TEAEs
- Fatal TEAEs
- Treatment related TEAEs according to the Principle Investigator
- Procedures related TEAEs
- Serious treatment related TEAEs
- TEAEs for which the study was discontinued
- TEAEs for which the study drug was discontinued
- TEAEs for which the study drug was interrupted
- TEAEs of special interest
- IRR events
- Serious IRR events
- Hypersensitivity events

Tables on TEAEs, serious TEAEs and hypersensitivity events will be repeated by ADA patient classification and by NAb patient classification.

All AEs, including pre-treatment events will be listed.

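### Infusion-related reactions can be counted only near an infusion but are reported per patient and per patient-year; rates per 100 infusions, split by dosing period, should be added

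*SAP*

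**What the plan says.** **Definition.** SAP 5.1.2 defines an IRR as an adverse event whose preferred term lies in one of three broad SMQ selections, "AND occurring within 48 hours of an infusion, or within 2 days in case no AE start time is available".

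**Reporting.** SAP 5.1.3 states: "An overview table will show the number and percentage of patients with at least 1 event and the number of events for the following". IRR events are on that list. It continues: "In addition, the number of events per patient years on study will be added to the overview table". SAP 5.1.2 defines the rate as events "divided by the sum of follow-up time (duration of treatment + FU phase) of all patients per treatment expressed in years". Under SAP 2.4.3, "All tables will be presented per treatment, unless specified otherwise". IRRs and serious IRRs are also tabulated by system organ class and preferred term. No IRR table uses infusions as denominator or is split by dosing frequency.

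**Dosing.** Under Protocol 5.4.1 every patient is scheduled weekly at visits 1 to 4. From visits 5 to 16 the frequency follows the individual platelet count in either arm. One rule begins "Reduce from weekly to q2w in patients achieving platelet counts of" at least 100×10^9/L, another returns patients to weekly, and doses are withheld above 400×10^9/L. From visit 17 the frequency is fixed, with listed exceptions. Patients who stop treatment but stay in the trial keep attending weekly (Protocol 4.4.2). A dose due at a visit with IVIg or anti-D rescue is withheld until the next visit (Protocol 6.8.4).

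**Infusion counts.** SAP 3.6.2 derives "Number of administrations: sum of all administrations of study drug", and SAP 3.6.3 summarises it. It is not linked to the IRR tables.

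**The concern.** Each infusion opens one window in which an IRR can be recorded, so the number of infusions is the natural exposure. Calendar time is not: it includes the follow-up phase and the visits after treatment has stopped, when few or no windows are open. The number of patients takes no account of how many windows each one had.

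This would not matter if infusion counts were balanced between arms. They need not be. The move to q2w and the withholding of doses at high counts follow platelet response, which the trial expects to differ by arm. Stopping treatment after more than three rescue occurrences, and doses withheld at rescue, follow lack of response. A reader who takes the arm contrast as a comparison of risk per infusion may therefore be misled. The broad SMQ terms add to this, because coincidental background events are captured in proportion to the number of windows.

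**Working it through.** The documents give no expected IRR rate, infusion count or q2w share, so there is no planned figure to reproduce. Infusion counts below follow from the visit rules; shares and risks are assumptions and are marked as such.

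**1. Windows per patient.** The window is taken as 2 days after each infusion, over a 24-week period of 168 days.
- Weekly throughout: 24 infusions; 2 × 24 / 168 = 28.6% of days.
- q2w from visit 5, the earliest point: 4 + 10 = 14 infusions; 2 × 14 / 168 = 16.7% of days; ratio 14 / 24 = 0.58.
- Switch at visit 16: 19 or 20 infusions; ratio 0.79 to 0.83.

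**2. Patient-level risk.** With risk r per infusion, the chance of at least one IRR is 1 − (1 − r)^n. At an assumed r = 0.005 this is 0.113 for n = 24 and 0.068 for n = 14, a ratio of 0.60. Over r = 0.002 to 0.02 the ratio runs from 0.59 to 0.64.

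**3. Arm-level events per patient-year at equal risk per infusion.** With equal follow-up, the ratio equals the ratio of mean infusions. If a share p switches at visit 5 and stays on q2w, the mean is 24 − 10p. Assume p = 5% on placebo (mean 23.5):

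| q2w share on efgartigimod (assumed) | Mean infusions | Ratio to placebo |
|---|---|---|
| 5% | 23.5 | 1.00 |
| 10% | 23.0 | 0.98 |
| 20% | 22.0 | 0.94 |
| 30% | 21.0 | 0.89 |
| 50% | 19.0 | 0.81 |

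The percentage of patients with an IRR gives nearly the same ratios at r = 0.005: 0.98, 0.94, 0.90 and 0.82 for shares of 10%, 20%, 30% and 50%.

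**4. Treatment stops on placebo.** Suppose an extra share s of placebo patients stops treatment at about visit 12, losing 12 infusions each, but stays in the trial. The placebo mean becomes 23.5 − 12s. With q2w shares of 20% and 5%:
- s = 12.5%: 22.0 / (23.5 − 1.5) = 1.00
- s = 20%: 22.0 / (23.5 − 2.4) = 1.04

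The direction is therefore not fixed.

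**5. Early concentration of risk.** If a fraction f of a weekly patient's reactions falls in the first four infusions, a patient on q2w from visit 5 has f + (1 − f) × 10/20 of the weekly patient's events: 0.75 at f = 0.5 and 0.90 at f = 0.8.

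**6. Does a per-infusion rate repair this?** If risk is constant across infusions, the ratio is 1.00 whatever the dosing pattern. If it is not, a pooled rate fails in the other direction. Assume f = 0.8, with 40% of efgartigimod patients on q2w from visit 5 and none on placebo.
- Events: 1 − 0.4 × (1 − 0.90) = 0.96 of placebo.
- Infusions: (0.6 × 24 + 0.4 × 14) / 24 = 20 / 24 = 0.83 of placebo.
- Pooled per-infusion ratio: 0.96 / 0.83 = about 1.15, a spurious excess.

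Split by period, the same example behaves. In visits 1 to 4, events and infusions are equal, so the ratio is 1.00. In visits 5 to 24, events are 0.6 + 0.4 × 0.5 = 0.80 of placebo and infusions are (0.6 × 20 + 0.4 × 10) / 20 = 0.80, so the ratio is again 1.00. This assumes constant risk within each period.

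**The case against.** The strongest reply is that fewer reactions after fewer infusions is a real property of a response-guided regimen. The per-patient percentage answers the question of what a patient treated this way experiences. That stands, and it is why the per-patient tables should stay. What can mislead is reading those figures, or the patient-year rate, as risk per infusion, together with the background events picked up by chance.

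Second, safety is summarised descriptively (Protocol 8.4.5), so no test depends on this. The trial is also small for the purpose. At most 117 + 39 = 156 patients are planned and "will be randomized in a 2:1 ratio to receive efgartigimod or placebo", that is 104 and 52. If 10 and 5 of them had an IRR (an assumption), the 95% interval for the risk ratio would be about 0.36 to 2.8, far wider than the shifts above. This stands and limits the severity.

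Third, the raw material is available. Administrations and q2w duration are summarised, IRRs are listed individually, and hypersensitivity events are tabulated without a time window. This covers the gap only in part. The hypersensitivity table does not include the extravasation terms, and a mean number of administrations is not an IRR rate.

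Fourth, a pooled per-infusion rate can itself mislead, as step 6 shows. That also stands and shapes the fix.

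**Conclusion.** The point holds as a minor reporting gap. IRRs arise only near infusions, both planned denominators ignore the number of infusions, and the patient-year denominator adds time with few or no windows. At equal risk per infusion the patient-year ratio could lie at about 0.81 to 1.04. That range rests on assumed q2w shares of 10% to 50% against 5%, a switch at the earliest visit with no return to weekly, and, at the upper end, a 20-point placebo excess of treatment stops with a 20% q2w share on efgartigimod. Early concentration of reactions would shrink the q2w effect.

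A reader might go further and infer that the efgartigimod arm is moved to q2w and must show a lower IRR rate. The documents do not support this. Frequency changes are made patient by patient in either arm and can be reversed. Treatment stops and doses withheld at rescue can remove windows on placebo too. Nor do IRR windows thin out over time for everyone: they stay constant for a patient on weekly dosing and become sparser only with q2w, withheld or stopped doses.

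**What to change.** In SAP 5.1.3, keep the per-patient IRR tables and add a descriptive summary of IRR events per 100 infusions by arm. Use administrations as derived in SAP 3.6.2 for the denominator, counted within period, and show visits 1 to 4 (all patients scheduled weekly) separately from visits 5 to 24. State that each IRR is assigned to the period of the infusion that opened its window. Do not make a single pooled per-infusion rate the main comparison between arms, because risk may be concentrated in the early infusions.

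The cost is SAP wording and a few table rows, using administration dates and times already recorded (SAP 3.6.1). The drawback is sparse counts within each period, so the rates should be shown with their event and infusion numbers. No dose, schedule or clinical rule changes.
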